- Assessment for signs and symptoms of thromboembolic events every 24 (± 2) hours from completion of the procedure until 48 (± 4) hours and 28 (± 3) days after last dose of LR769, to include checking for any signs or symptoms of thromboembolic events, such as pulmonary embolism (PE) (e.g., shortness of breath, chest pain, cyanosis) or deep vein thrombosis (e.g., calf pain, swelling/edema, redness, venous distension, pain on dorsiflexion)
- Postoperative assessment performed on all patients while hospitalized every 24 (± 2) hours from completion of the procedure until 48 (± 4) hours after last dose of LR769 (unless discharged from the hospital sooner) to include checking patient's incision or procedure site for inflammation, bleeding, infection, oozing, discoloration
- Clinical safety laboratory tests (chemistry, hematology and urinalysis) at screening, 24 (± 2) hours after completion of the procedure, and during follow up
- Vital signs (blood pressure, heart rate, respiratory rate, and body temperature) at screening, just prior to the surgical or other invasive procedure, 24 (± 2) hours after completion of the procedure, and follow up at 48 (± 4) hours after last dose of LR769
- Electrocardiogram (ECG) at screening
- AEs recorded throughout the study
- Immunogenicity of LR769 at pre-procedure and during follow-up visits

Statistical Methods:

All data collected in this study will be displayed using summary tables and patient data listings. Continuous variables will be summarized using descriptive statistics, specifically the mean, median, standard deviation, minimum, and maximum. Categorical variables will be summarized by frequencies and percentages.

Analysis Populations:

The Efficacy Population is defined as all patients who receive LR769 treatment, undergo a surgical or invasive procedure, and have at least 1 efficacy assessment. The Safety Population is defined as all patients who receive at least 1 dose of LR769. All efficacy analyses will be performed on the Efficacy Population and all safety analyses will be performed on the Safety Population.

Sample Size Determination:

The sample size was determined based on adaptations of international guidelines for coagulation factors and after US and EU health authority consultations.

Efficacy Evaluations:

Primary efficacy endpoint:

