^a Screening visit will be split into 2 different days if the total volume of blood drawn is to exceed 0.8 mL/kg at a single time.

Table 5 includes estimates for the amount of blood to be drawn for pediatric patients who weigh ≥ 27 kg.

Table 5. Total Amounts (mL) of Blood Taken During the Study for Pediatric Patients ≥ 27 kg

	Screen	Pre Surgery	24 hrs post procedure	7-14 days post first dose	48 hrs post last dose	28 days post last dose/EOS
Hematology	2		3		3	3
PT and aPTT and Factors VIII and IX and Inhibitors (local lab)	6					
Serology	4					
Chemistry	4		5		5	5
Factors VIII or IX and Inhibitors (central lab)	4.2					
Immunogenicity and serum storage sample		3				4
Immunogenicity				2	2	
Totals	20.2	3	8	2	10	12

EOS = end of study

Table 6 includes estimates for the amount of blood to be drawn for adult patients (≥ 18 years old).

Table 6. Total Amounts (mL) of Blood Taken During the Study for Adult Patients (≥ 18 Years)

	Screen	Pre surgery	24 hours post procedure	7-14 days post first dose	48 hours post last dose	28 days post last dose/EOS
Hematology	4		4		4	4
PT and aPTT and Factors VIII and IX and Inhibitors (local lab)	8					
Serology	6					
Chemistry	8		8		5	5
Factors VIII or IX and Inhibitors (central lab)	5.7					
Immunogenicity, serum storage sample		5				5
Immunogenicity				3	3	
Totals	31.7	5	12	3	12	14

EOS = end of study

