6.6.1 Laboratory Parameters

6.6.1.1 Clinical Safety Laboratory Tests

The clinical safety laboratory tests for patients ≥ 12 kg are presented in [Table 7](#) and will be carried out by the local laboratory of the site (FVIII or FIX concentration as well as inhibitor testing will also be analyzed at the central laboratory) at Screening. Hematology, chemistry, and urinalysis will be repeated as specified in [Appendix 1](#).

Table 7. List of Laboratory Tests

Hematology:	Serum Chemistry:

- Hematocrit (Hct)- Hemoglobin (Hgb)- Platelet count- Red blood cell (RBC) count- White blood cell (WBC) count with differential (automated)- CD4 count¹	
- Albumin (ALB)- Alkaline phosphatase (ALK-P)- Alanine aminotransferase (ALT; SGPT)- Aspartate aminotransferase (AST; SGOT)- Blood urea nitrogen (BUN) or urea- Calcium (Ca)- Chloride (Cl)- Creatinine- Gamma-glutamyl transferase (GGT)- Glucose- Lactate dehydrogenase (LDH)- Potassium (K)- Sodium (Na)- Total bilirubin- Total protein- Troponins
Urinalysis (dipstick): 
- Glucose- Ketones- Microscopic examination of sediment in case of positive dipstick- Nitrite- Occult blood- Protein	
Serology ¹ 
- Hepatitis B surface antigen (HBsAg)- Hepatitis C virus (HCV)- Human immunodeficiency virus (HIV)	Coagulation ¹ : 
- FVIII² or FIX³- FVIII² or FIX³ inhibitors- Prothrombin time (PT)- Activated partial thromboplastin time (aPTT)

Note: laboratory tests may vary depending on the weight of the patient (see [Section 6.6](#)).

¹ At Screening only

² In hemophilia A patients only

³ In hemophilia B patients only

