7.2 Surgery/Invasive Procedure and LR769 Treatment

7.2.1 Before Surgery/Invasive Procedure

- Confirm eligibility
- Physical examination (excluding height, including weight, which is the weight to be used for calculating dose of LR769) within 24 hours before the procedure
- An IV bolus dose of 75 µg/kg (for a minor surgery or other minor invasive procedure) or 200 µg/kg (for a major surgery or other major invasive procedure) of LR769 administered within ≤2 minutes before the surgical incision or start of the invasive procedure.
- Predicted surgery/invasive procedure characteristics
- Vital signs (blood pressure, heart rate, respiratory rate, and body temperature [sublingual or tympanic])
- Assessment of concomitant medications
- Assessment of AEs
- Immunogenicity sample (including storage serum sample for future use)

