9.5.2 Secondary Efficacy Endpoints

The secondary efficacy endpoints are:

- Percentages of success as defined as the combination of “good” and “excellent” responses by the investigator or designee for all efficacy timepoints other than the primary
- Percentages of “poor,” “moderate,” “good,” and “excellent” response by the investigator or designee for all efficacy timepoints
- Percentages of success as defined as the combination of “good” and “excellent” responses by the surgeon/practitioner
- Percentages of “poor,” “moderate,” “good,” and “excellent” response by the surgeon/practitioner for the intraoperative period
- Intraoperative blood loss determined by the surgeon/practitioner as compared to the surgeon/practitioner’s maximum predicted blood loss
- Number of events requiring transfusion between start of procedure and 48 (\pm 4) hours after last administration of LR769
- Changes in hemoglobin between start of procedure and 48 (\pm 4) hours after last administration of LR769
- Amount of LR769 used. Total, and separated by use in hospital, at home, or for specific reasons (eg, physical therapy, or other reasons like drain or suture removal)
- Number and type of bleeding episodes at the surgical site between start of procedure and 48 (\pm 4) hours after last administration of LR769
- Number of surgical interventions/re-explorations for bleeding episodes between start of procedure and 48 (\pm 4) hours after last administration of LR769

Point estimates will be computed together with 95% confidence intervals for the proportion of successes, mean difference between intraoperative blood loss and surgeon/practitioner’s maximum predicted blood loss, proportion of events requiring transfusion, mean hemoglobin level at each timepoint, mean amount of LR769 used, and mean number of surgical interventions/re-explorations for bleeding episodes. Clopper-Pearson exact confidence intervals will be used for dichotomous endpoints; confidence intervals for continuous variables will be based on the normal approximation.

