Appendix 1 Schedule of Events

Evaluation	Screening Days -21 to -1	Procedures + LR769 Treatment						Follow-Up Visits		
		Pre Procedure	Immediately Postoperative	24 (±2) hrs after procedure completion	Every 24 (±2) hrs after procedure completion	7-14 days after 1 st dose of LR769 ⁹	Last Dose of LR769	Early Termination	48 (±4) hrs after last dose	28 (±3) days after last dose
Informed Consent	X									
Inclusion/Exclusion Criteria	X	X								
Demographics and Detailed Medical History	X									
Physical Examination ¹	X	X ⁸						X	X	
Safety Lab Tests										
Hematology, chemistry, urinalysis (local lab)	X			X				X	X	X
Coagulation ¹⁰ , serology ¹²	X									
LR769 Administration ²		X								
Surgical/Invasive Procedure Characteristics ³		X	X							
Postoperative Assessment ⁴				X	X		X	X	X	
Vital Signs ⁵	X	X		X				X	X	
12-Lead ECG	X									

Evaluation	Screening Days -21 to -1	Procedures + LR769 Treatment						Follow-Up Visits		
		Pre Procedure	Immediately Postoperative	24 (±2) hrs after procedure completion	Every 24 (±2) hrs after procedure completion	7-14 days after 1 st dose of LR769 ⁹	Last Dose of LR769	Early Termination	48 (±4) hrs after last dose	28 (±3) days after last dose
Efficacy Assessments ⁶										
Surgeon's Assessment			X							
Investigator's Assessment				X	X		X	X	X	
Adverse Event Assessment	X	X ¹⁰								
Concomitant Medication	X	X								
Immunogenicity		X ⁷				X ⁹		X ⁷	X	X ⁷

¹ Height will be measured at screening only.

² Initial dose of 75 µg/kg (minor surgery or other minor invasive procedure) or 200 µg/kg (major surgery or other major invasive procedure) of LR769 will be administered as an IV bolus dose within ≤2 minutes prior to surgical incision or start of the invasive procedure; subsequent doses of 75 µg/kg of LR769 will be administered as an IV bolus dose of LR769 within ≤2 minutes during and after surgical or other invasive procedure; duration of treatment will be dependent on the type of procedure and the patient's status in accordance with [Table 1](#) and [Table 2](#).

³ Surgical/invasive procedure characteristics: Predicted surgery/invasive procedure characteristics: major or minor, maximum expected blood loss in a patient without hemophilia, type of anesthesia. Actual surgery/invasive procedure characteristics: major or minor, duration, estimated blood loss, factors that may have influenced bleeding independent of hemostasis, actual type of anesthesia, and complications.

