7.2 Definition of Baseline, Study Visits, and Visit Windows

Baseline is defined as the last available assessment prior to first study drug dose.

For Post-Operative assessments timepoints will be assigned according to Protocol-specified visit windows. Assessment occurring 24 (\pm 2) hours from procedure completion will be assigned to the 24-hour timepoint, and so on every 24 hours, creating timepoints for 48, 72... hours.

All other analyses will use the visits and time points as reported in the eCRF. No further reassignment of the visits will be done.

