7.7.2 Analysis of Secondary Efficacy Endpoints

The following endpoints are considered secondary for this study:

- Percentages of success as defined as the combination of “good” and “excellent” responses by the investigator or designee for all efficacy timepoints other than the primary
- Percentages of “poor,” “moderate,” “good,” and “excellent” response by the investigator or designee for all efficacy timepoints
- Percentages of success as defined as the combination of “good” and “excellent” responses by the surgeon/practitioner for the intraoperative period
- Percentages of “poor,” “moderate,” “good,” and “excellent” response by the surgeon/practitioner for the intraoperative period
- Intraoperative blood loss determined by the surgeon/practitioner as compared to the surgeon/practitioner’s maximum predicted blood loss
- Number of events requiring transfusion between start of procedure and 48 (±4) hours after last administration of LR769
- Changes in hemoglobin between start of procedure and 48 (±4) hours after last administration of LR769
- Amount of LR769 used. Total, and separated by use in hospital, at home, or for specific reasons (eg, physical therapy, or other reasons like drain or suture removal)
- Number and type of bleeding episodes at the surgical site between start of procedure and 48 (±4) hours after last administration of LR769
- Number of surgical interventions/re-explorations for bleeding episodes between start of procedure and 48 (±4) hours after last administration of LR769

The first four secondary endpoints will be analyzed similarly to the primary endpoint: numbers and percentages of successes will be summarized at each timepoint, together with their Clopper-Pearson exact confidence limits.

Difference between the expected and actual blood loss will be calculated for each surgery in the study and then summarized together with 95% confidence limits. Number of events requiring transfusion, Number of bleeding episodes (by type) at the surgical site between start of procedure and 48 (±4) hours, and Number of surgical interventions/re-explorations for bleeding episodes between start of procedure and 48 (±4) hours after last administration of LR769 will be analyzed similarly.

Hemoglobin levels will be summarized at baseline and at 48 (±4) hours after last administration of LR769. Changes from baseline will also be summarized for 48 (±4) hours timepoint. 95% confidence limits for the changes will be displayed.

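### The hemoglobin endpoint starts at the procedure, but no hemoglobin is scheduled then; on scheduled data its baseline is a screening value 1 to 21 days old

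*Protocol*

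**What the plan says.** The endpoint is worded the same way in the Protocol synopsis, Protocol 6.8.1 and 9.5.2, and SAP 5 and 7.7.2: "Changes in hemoglobin between start of procedure and 48" (±4) hours after the last dose.

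The measurements behind it are set elsewhere:

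- Protocol Table 7 (6.6.1.1) places "Hemoglobin (Hgb") in the hematology panel.
- The synopsis, under Safety Assessments, has "Clinical safety laboratory tests (chemistry, hematology and urinalysis) at screening, 24" (±2) hours after the procedure, and during follow-up.
- In Appendix 1 the row "Hematology, chemistry, urinalysis (local lab") is marked at screening, 24 hours, early termination, 48 hours after the last dose and 28 days after the last dose. The Pre Procedure and Immediately Postoperative cells are blank.
- The only blood sample that Protocol 7.2.1 lists before the procedure is "Immunogenicity sample (including storage serum sample for future use"). In the adult volume table (Table 6), the only row with a pre-surgery entry is "Immunogenicity, serum storage sample".

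On the analysis side, SAP 7.2 states: "Baseline is defined as the last available assessment prior to first study drug dose". SAP 7.7.2 applies this: "Hemoglobin levels will be summarized at baseline" and again at 48 hours after the last dose, with 95% confidence limits for the change.

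**The concern.** The endpoint is meant to show how much hemoglobin falls over the operation and the treated recovery. That needs a value taken at, or just before, the start. If the first value comes from screening, anything that moved hemoglobin between screening and surgery is counted as perioperative change.

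The documents leave room for such movement. Protocol 5.6.2 requires only 24 hours between the last FVIIa-containing product and the first LR769 dose. Exclusion criterion 7 exempts patients from other LR769 studies, including studies that treat bleeding episodes. A bleed between screening and surgery is therefore possible. Weight, vital signs and the physical examination are repeated before the procedure (Protocol 7.2.1); the laboratory value that anchors an efficacy endpoint is not.

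The stake is interpretive. In a single-arm, open-label study whose primary outcome is an investigator's rating, a laboratory measure is a useful companion, provided it covers the interval it names.

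**Working it through.** The plan gives no figure to reproduce. The check is a comparison of schedules followed by day counts.

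**1. Where hematology is scheduled.**

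| Source (Protocol) | Screening | Before procedure | 24 h after procedure | 48 h after last dose | 28 days after last dose |
|---|---|---|---|---|---|
| Sections 7.1, 7.2.1, 7.3.1, 7.6.1, 7.6.2 | yes | no | yes | yes | yes |
| Tables 3 to 6 | yes | blank in all four | yes | yes | yes |
| Appendix 1 | yes | blank | yes | yes | yes |

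The synopsis fits the same pattern. Text, volume tables and schedule agree, so the gap is not damage from reading the PDF.

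**2. What the baseline rule selects.** The first LR769 dose is given just before incision, so the last value before the first dose would serve well as a start-of-procedure value if one were drawn. The only scheduled candidate is screening, Days -21 to -1 (Protocol 7.1). Age of baseline at the procedure: 1 to 21 days.

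**3. Share of the analysed interval that precedes surgery.** Inputs: minimum treatment of 5 days for major procedures (Protocol 5.2.2) and 2 days for minor (5.2.3), plus 2 days to the final assessment; procedure time is ignored. Share = screening age / (screening age + treatment + 2).

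- Major, oldest screening: 21 / (21 + 5 + 2) = 21/28 = 75%. Newest: 1 / (1 + 5 + 2) = 1/8 = 12.5%.
- Minor, oldest screening: 21 / (21 + 2 + 2) = 21/25 = 84%. Newest: 1 / (1 + 2 + 2) = 1/5 = 20%.
- The interval the endpoint names is 5 + 2 = 7 days for major and 2 + 2 = 4 days for minor.

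Longer treatment lowers these shares; the shorter treatment allowed for some minor procedures raises them.

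**4. Room for one more sample.** At the scheduled volumes, hematology takes 1 mL in Table 4, 2 to 3 mL in Table 5 and 4 mL in Table 6. The pre-surgery draw would become:

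- Table 4: 3 + 1 = 4 mL.
- Table 5: 3 + 2 or 3 = 5 to 6 mL.
- Table 6: 5 + 4 = 9 mL.

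The tight case is the lightest child in Table 4. Its footnote splits screening above 0.8 mL/kg. If that stands for the 1% single-draw limit (an assumption), the 3% four-week limit is 3 × 0.8 = 2.4 mL/kg, or 28.8 mL at 12 kg. Draws from screening to 48 hours after the last dose total 15.7 + 3 + 3 + 2 + 5 = 28.7 mL, and can fall within four weeks. One more mL gives 29.7 mL, above the limit for weights below 29.7 / 2.4 = 12.4 kg.

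**The case against.** **The baseline rule is open to fresher values.** SAP 7.2 takes whatever was last available, so a routine pre-operative hemoglobin entered in the eCRF would become the baseline. This stands. A reader might infer that every analysed change will start from a three-week-old value; the documents do not support that. Twenty-one days is the edge of the window, and the typical age is unknown. Equally, neither document asks for a later value.

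**Nothing is hidden.** A reader might infer that the SAP swaps in screening without saying so. It does not: Protocol 9.6 and SAP 7.2 both define baseline, and SAP 7.7.2 says that the change is from baseline. What remains is that the endpoint's label and the schedule do not match.

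**The endpoint carries little weight.** It is one of ten secondary endpoints, efficacy results are descriptive (Protocol 9.5), and hemoglobin is not named among the inputs to the primary rating. Transfusion events, re-explorations and drug use are reported as well. Adverse events are collected from consent, and concomitant therapies from 30 days before screening, so reported pre-operative bleeds and treatment can be traced. All of this stands and limits the importance of the point.

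**Transfusion.** Because transfusion raises the later value, a reader might ask for the change to be split by transfusion status. The plan already analyses transfusion events over the same interval and lists each transfusion (SAP 7.7.2). With a minimum of 12 procedures, a further split would leave very small cells. It is a preference, not a defect.

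**Conclusion.** The mismatch is established from the documents: the endpoint names an interval that the schedule does not measure. On scheduled data, the baseline is 1 to 21 days old, and up to 75% (major) or 84% (minor) of the analysed interval can lie before surgery. Those two maxima assume screening on Day -21, minimum treatment, and no later value captured.

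A reader might wish to state the loss of precision as a standard error. That needs a within-patient standard deviation for hemoglobin, which the documents do not give, and the extra variance would combine with the perioperative variance rather than add directly to the standard error. No such figure is offered, nor a direction or size for any pre-operative drift.

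The effect is confined to one descriptive secondary endpoint. It is worth correcting because the remedy is small.

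**What to change.** - **Protocol.** Add hemoglobin to the Pre Procedure column of Appendix 1, to Section 7.2.1 and to Tables 4 to 6, as a separate tube at the immunogenicity venepuncture and before the first dose.
- **Patients under 12 kg.** Record the site's routine pre-operative hemoglobin in the eCRF instead, given the limits in Section 6.6. The same route suits the lightest children in Table 4 if the individually calculated volume leaves no room.
- **SAP 7.2 and 7.7.2.** Use this value as the hemoglobin baseline, and state that baseline is set for each procedure. Patients may enter more than once (SAP 7.1), and the present reference to the first dose does not say of which procedure.
- **If the value cannot be obtained.** Relabel the endpoint *change from screening/baseline* in both documents and report the age of the baseline sample. This remains possible after enrolment, since SAP 7.1 allows updates before database lock.

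The cost is 1 to 4 mL of blood at an existing draw, or one extra eCRF field; the fallback costs only wording. Changing the schedule needs a protocol amendment.

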- Percentage of surgical or other invasive procedures with a “good” or “excellent” response to LR769 treatment 48 (\pm 4) hours after the last administration of LR769 as assessed by the investigator.

A point estimate of this endpoint will be calculated together with a Clopper-Pearson exact 95% confidence interval.

Secondary efficacy endpoints:

- Percentages of success as defined as the combination of “good” and “excellent” responses by the investigator or designee for all efficacy timepoints other than the primary
- Percentages of “poor,” “moderate,” “good,” and “excellent” response by the investigator or designee for all efficacy timepoints
- Percentages of success as defined as the combination of “good” and “excellent” responses by the surgeon/practitioner
- Percentages of “poor,” “moderate,” “good,” and “excellent” response by the surgeon/practitioner for the intraoperative period
- Intraoperative blood loss determined by the surgeon/practitioner as compared to the surgeon/practitioner’s maximum predicted blood loss
- Number of events requiring transfusion between start of procedure and 48 (\pm 4) hours after last administration of LR769
- Changes in hemoglobin between start of procedure and 48 (\pm 4) hours after last administration of LR769
- Amount of LR769 used. Total, and separated by use in hospital, at home, or for specific reasons (eg, physical therapy, or other reasons like drain or suture removal)
- Number and type of bleeding episodes at the surgical site between start of procedure and 48 (\pm 4) hours after last administration of LR769
- Number of surgical interventions/re-explorations for bleeding episodes between start of procedure and 48 (\pm 4) hours after last administration of LR769

Point estimates will be computed together with 95% confidence intervals for the proportion of successes, mean difference between intraoperative blood loss and surgeon/practitioner’s maximum predicted blood loss, proportion of events requiring transfusion, mean hemoglobin level at each time point, mean number of bleeding episodes, mean amount of LR769 used, and mean number of surgical interventions/re-explorations for bleeding episodes. Clopper-Pearson exact confidence intervals will be used for dichotomous endpoints; confidence intervals for continuous variables will be based on the normal approximation.

Safety Evaluations

Safety endpoints include the following:

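### No interval method is named for the bleeding, re-exploration and transfusion counts, and the mean-based interval reached by inference is 0 to 0 when no event occurs (minor)

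*Protocol*

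**What the plan says.** Protocol 9.5.2 requires 95% intervals for a list of secondary summaries that ends with "mean amount of LR769 used, and mean number of surgical interventions/re-explorations for bleeding episodes". The matching list in the synopsis has one more entry, since it reads "mean number of bleeding episodes, mean amount of LR769 used" before going on to re-explorations. Section 9.5.2 does not ask for an interval on bleeding episodes.

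Both places give the same two methods: "Clopper-Pearson exact confidence intervals will be used for dichotomous endpoints", and "confidence intervals for continuous variables will be based on the normal approximation". Neither mentions counts.

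Transfusion appears in two forms within Protocol 9.5.2. The endpoint list has "Number of events requiring transfusion between start of procedure". The interval list has "proportion of events requiring transfusion", with no denominator stated.

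SAP 7.7.2 applies Clopper-Pearson to the first four secondary endpoints, which are the response ratings. The blood-loss difference is calculated per surgery and "summarized together with 95% confidence limits". The SAP then lists "Number of events requiring transfusion, Number of bleeding episodes (by type) at the surgical site" together with the number of re-explorations, and says that these are analysed in the same way. It names no method for those limits. SAP section 9 records one departure from the protocol, the dropped paired t-tests.

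**The concern.** A count of re-explorations or bleeding episodes per procedure is neither dichotomous nor continuous. With two methods on offer, a programmer would most naturally take the mean-based one, and the SAP's link to the blood-loss difference points the same way. That interval takes its width from the sample standard deviation. If no procedure has an event, the standard deviation is zero and the interval has no width.

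This is a realistic outcome. The study may stop at 12 procedures, 6 of them major (SAP section 4). SAP 7.7 reports efficacy by surgery type and overall, then again by age group, and bleeding episodes are further split by type. Each split makes an all-zero cell more likely. A 95% interval printed as 0 to 0 from 6 or 12 procedures would express certainty that such data cannot give.

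**Working it through.** The plan states no event rate, interval width or power for these endpoints, so there is no figure to reproduce.

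**Inputs.** Confidence level 95%, two-sided (Protocol 9.5.2). Minimum n = 12 procedures overall and n = 6 major (SAP section 4). Event rates are not given. I assume Poisson means of 0.05, 0.1, 0.2 and 0.5 events per procedure.

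**Mean-based interval.** Mean ± q × SD/√n, with q = 1.96 or the t quantile on n − 1 degrees of freedom.

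- No events: mean = 0 and SD = 0, so the interval is 0 to 0 for either q and any n ≥ 2.
- One event: mean = 1/n and SD/√n = 1/n. With z, n = 12 gives 0.083 ± 1.96 × 0.083, or −0.080 to 0.247. n = 6 gives 0.167 ± 1.96 × 0.167, or −0.160 to 0.493. The negative lower limit is a lesser symptom.

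**Exact limits with no events.**

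- Clopper-Pearson upper limit for the proportion of procedures with any event, 1 − 0.025^(1/n): 1 − 0.735 = 26.5% at n = 12 and 1 − 0.541 = 45.9% at n = 6.
- Exact Poisson upper limit for the mean, −ln(0.025)/n: 3.689/12 = 0.31 and 3.689/6 = 0.61 per procedure.

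The first is a limit on a proportion and the second on a mean count. Only the second has the same target as the mean-based interval.

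**How often, and at what cost in coverage.** P(all zero) = exp(−n × mean). Coverage is by simulation under independent Poisson counts.

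| n | Assumed mean | P(all zero) | z coverage | t coverage | z coverage given ≥1 event |
|---|---|---|---|---|---|
| 6 | 0.05 | 74% | 26% | 26% | 99% |
| 6 | 0.1 | 55% | 45% | 45% | 99.8% |
| 6 | 0.2 | 30% | 69% | 70% | 98% |
| 6 | 0.5 | 5% | 78% | 95% | 82% |
| 12 | 0.05 | 55% | 45% | 45% | 99.6% |
| 12 | 0.1 | 30% | 70% | 70% | 99.5% |
| 12 | 0.2 | 9% | 90% | 91% | 99% |
| 12 | 0.5 | 0.2% | 92% | 93.5% | 92.5% |

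At means of 0.05 to 0.2 the shortfall is almost entirely the all-zero sample, which the t multiplier does not repair. At a mean of 0.5 with n = 6, t does repair it.

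**Check of the alternatives under clustering.** SAP 7.1 notes that a patient may enter more than once. I took 12 procedures as 2 in each of 6 patients, with an assumed gamma patient effect of mean 1 and variance 1 or 2.

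- Clopper-Pearson for any event covers 94% to 99% across the four means.
- Exact Poisson with variance 1 covers 97.0%, 98.5%, 97.0% and 86.5% at means 0.05, 0.1, 0.2 and 0.5.
- The t interval with variance 1 covers 43% to 86% at means 0.05 to 0.2, and about 86% at 0.5.
- With variance 2 and a mean of 0.5, exact Poisson covers 78.4% and t covers 80.0%.

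Clopper-Pearson therefore holds up. Exact Poisson is clearly better than t at low rates but no better at the highest rate with clustering.

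**The case against.** The strongest reply is that the plan never commits to a 0-to-0 interval. The protocol confines the normal approximation to continuous variables, the SAP names no method, and the table shells are a separate document. That stands: the method is inferred from a two-item list and a cross-reference.

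Second, a degenerate interval would not stand alone. SAP 7.1 requires n, mean, SD, median, minimum and maximum for continuous summaries, and 7.7.2 requires listings of transfusions, interventions and bleeding episodes. If the counts are summarised like the blood-loss difference, the same table shows SD 0 and maximum 0. That also stands, and it limits the harm, although it does not make the interval right.

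Third, the low coverage figures rest on assumed rates and mostly restate the chance of an all-zero sample. That is correct.

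Two stronger readings are tempting. A reader might infer that the SAP turned transfusion from a proportion into a count without recording it. The documents do not support that, because the count is the protocol's own endpoint wording and the protocol's two lists already disagree. A reader might also infer that these counts corroborate the investigator's rating independently. They do not: Protocol 9.5.1 makes bleeding episodes, interventions and transfusions inputs to that rating.

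**Conclusion.** The point holds as a minor one. No method suited to counts is named for re-explorations, for bleeding episodes, or for transfusion when analysed as a number. The mean-based interval that the text leads to has zero width when no event occurs, while exact upper limits at the planned minimum are 26.5% (0/12) and 45.9% (0/6) of procedures. The zero-width result and these limits are arithmetic and need no assumed rate. How often it would happen does: 9% to 55% at n = 12 and 30% to 74% at n = 6, for assumed means of 0.2 down to 0.05. If transfusion is read as a proportion of procedures, Clopper-Pearson applies and the problem does not arise for it.

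The documents do not support any doubt about the primary result on this ground. Protocol 9.5 makes efficacy reporting descriptive, no test or threshold rests on these counts, and the primary endpoint and response proportions keep exact intervals.

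Two wording conflicts remain whatever method is chosen: the synopsis against 9.5.2 on bleeding episodes, and the protocol's two descriptions of transfusion.

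**What to change.** In SAP 7.7.2, for each of transfusion, bleeding episodes and re-explorations, make the main summary the number and percentage of procedures with at least one event, with a Clopper-Pearson 95% interval. Add a table note that procedures are treated as independent although a patient may contribute several.

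If a mean count is also shown, give it without an interval, or with an exact Poisson interval and a note that it undercovers when events cluster within patients at higher rates.

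Define the transfusion endpoint per procedure, so that the protocol's number and proportion wordings agree. Settle between the synopsis and 9.5.2 whether bleeding episodes get an interval. Record these changes in SAP section 9.

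The cost is SAP wording, minor programming and wider intervals. No new data are needed. The Clopper-Pearson interval still ignores within-patient correlation, but its coverage stayed at 94% or above in the clustered settings checked.
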